4.3.5.2. Start and Stop Dates for Antiseizure and Rescue Medications

Missing and incomplete dates for concomitant anti-seizure medications and rescue medications will be imputed for the purpose of estimating the time of medication usage relative to study treatment.

The imputation rules for concomitant medication start dates are as follows:

- If the date is completely missing, the date will be imputed as the date of the subject's first dose of study drug;
- If only the day is missing, the date will be imputed as the date of the first dose of study drug if the concomitant medication start date is in the same month and year as the first dose of study drug; otherwise, the missing day will be imputed as the first day of the month;
- If both the day and month are missing, the date will be imputed as the date of the first dose of study drug if the concomitant medication start date is in the same year as the first dose of study drug; otherwise, the missing day and month will be imputed as 01 January.

If any of the above imputations result in a start date which is later than an existing (not imputed) medication stop date, the start date will be imputed as the stop date.

The imputation rules for concomitant medication stop dates are as follows:

- If the date is completely missing, the date will be imputed as the date of the subject's last dose of study drug;
- If only the day is missing, the date will be imputed as the date of the last dose of study drug if the concomitant medication stop date is in the same month and year as the last dose of study drug; otherwise, the missing day will be imputed as the last day of the month;
- If both the day and month are missing, the date will be imputed as the date of the last dose of study drug if the concomitant medication stop date is in the same year as the last dose of study drug; otherwise, the missing day and month will be imputed as 31 December.

If any of the above imputations result in a stop date which is earlier than an existing (not imputed) medication start date, the stop date will be imputed as the start date.

Missing and partial dates will not be imputed for other concomitant medications.

4.4. Coding Dictionaries

Medical history and AEs will be coded using the Medical Dictionary for Regulatory Activities (MedDRA, version 24.0). Prior and concomitant medications will be coded using the World Health Organization (WHO) Drug Dictionary (March 2020 B3 Global version).

5. STUDY POPULATION

5.1. Disposition

The summary of subject enrollment and disposition will include:

- The total number of subjects who provided informed consent and were screened
- The following categories will be presented by treatment group and overall. The number of subjects randomized will serve as the denominator to calculate percentages.
 - Randomized but not treated
 - Received study drug
 - Completed study drug dosing
 - Completed titration period
 - Completed maintenance period
 - Discontinued study drug dosing, including reasons
 - Completed study
 - Discontinued study, including reasons

5.2. Summary of Analysis Sets

A summary of the number and percentage of subjects included in (and excluded from, as applicable) each analysis set will be provided for each treatment group.

5.3. Protocol Deviations

Protocol deviations will be reviewed and tracked as described in the study-specific Protocol Deviation Plan. Prior to database lock, all major protocol deviations that have been entered into the clinical trial management system will be exported to a file and integrated into the study data.

The study team will review a listing of all major protocol deviations and determine which deviations are important protocol deviations (IPDs). IPD are protocol deviations that might significantly affect the completeness, accuracy and/or reliability of the study data or that might significantly affect a subject's rights, safety, or well-being. The assessment of IPDs will be performed prior to database lock and unblinding of the randomized treatment assignments.

A summary of the number and percentage of all randomized subjects with IPD by deviation category will be presented by treatment group and overall. The summary will be repeated for the subset of IPD that are related to the coronavirus disease 2019 (COVID-19) pandemic.

All major protocol deviations will be presented in a data listing and any that are classified as IPD will be flagged in the listing. Any major protocol deviations related to the COVID-19 pandemic will also be flagged in the listing.

5.4. Demographic and Baseline Characteristics

Demographics and study baseline (ie, last measurement collected prior to the first dose of study drug) characteristics will be summarized descriptively by treatment group and overall for the full analysis set. The following variables will be summarized:

- Demographics: age, sex, ethnicity, race, country
- Baseline subject characteristics: height [cm], weight [kg], body mass index [BMI, kg/m²]
- Baseline severity of illness: CGI-S
- Baseline seizures (yes/no)
- Baseline SWI during first hour of NREM sleep
- Medications: number of current antiseizure medications, number of prior antiseizure medications, rescue medications [yes/no], non-drug antiseizure treatments [yes/no]
- Seizure and CSWS history: age at CSWS diagnosis, duration since CSWS diagnosis, age at symptom onset for CSWS, etiologic subgroup (structural, genetic, unknown), seizure history [any, tonic-clonic, tonic, atonic, focal onset seizures (FOS) with an identifiable motor component, other], age at seizure onset, family history of seizure activity

6. IMPACT OF COVID-19 PANDEMIC

This section describes analyses and summaries that will be produced to help determine the potential impact of the COVID-19 pandemic on the study conduct/data and additional details regarding how data that is potentially impacted by the COVID-19 pandemic will be handled in the analysis plan. It is in alignment with the guidance put forth by the US Food and Drug Administration (FDA; Conduct of Clinical Trials of Medical Products During the COVID-19 Public Health Emergency [March 2020, updated January 2021]) and European Medicines Agency (EMA; Points to consider on implications of Coronavirus disease [COVID-19] on methodological aspects of ongoing clinical trials [March 2020]).

To help understand the impact of the COVID-19 pandemic on the clinical trial data, the following listings will be generated:

- A listing of all subjects affected by the COVID-19 pandemic. The listing will identify subjects who experience at least one of the following situations due to the COVID-19 pandemic (additional situations may be included):
 - Discontinued study due to COVID-19
 - Presumed or confirmed diagnosis of COVID-19
 - Had at least one COVID-19 pandemic-related major protocol deviation
 - Missed at least one study visit or assessment due to COVID-19
 - Required at least one assessment to be collected using a method other than what is defined in the protocol (eg, remotely) due to COVID-19
- A listing of subjects who withdrew from study due to the COVID-19 pandemic, which will include the specific reasons.
- A listing by subject of visits and assessments affected by the COVID-19 pandemic (eg, missing, partial, collected remotely).

The above listings may be omitted if it is known there was no impact of the COVID-19 pandemic on the study conduct.

The broad Standardised MedDRA Query (SMQ) of COVID-19 will be utilized to identify preferred terms (PTs) pertaining to subjects with a presumed or confirmed diagnosis of COVID 19 (using MedDRA version 24.0).

7. EFFICACY

The efficacy endpoints and planned analysis methods are described below. Unless otherwise noted, the full analysis set will be used for all efficacy analyses, and descriptive statistics for observed values and changes from baseline will be presented by treatment group (NBI-827104 versus placebo) and nominal visit according to the protocol schedule of assessments.

7.1. Multiple Comparisons and Multiplicity

There will be no adjustments for multiple comparisons.

[figure not shown]
7.2. Statistical Models

7.2.1. Continuous endpoints

The continuous efficacy endpoints will be analyzed using an analysis of covariance (ANCOVA) model, which includes the change from baseline to the respective postbaseline visit where the endpoint is being evaluated. The model will include the relevant baseline value as a covariate, and treatment group (NBI-827104; placebo). The treatment group difference at the postbaseline visit and the 90% CIs will be obtained from the ANCOVA model.

For endpoint data departing from the normal distribution, values will be log-transformed prior to analysis including the baseline covariate. The estimates of the mean differences between treatment groups will be exponentiated to original units and reported as geometric mean ratios (as a percent). The 2-sided 90% CIs associated with each difference will be calculated and exponentiated back to original units (displayed as percentages) for reporting purposes.

An example of the SAS software code is provided below.

7.2.2. Categorical endpoints

Ordinal categorical efficacy endpoints will be analyzed using the Jonckheere-Terpstra test to compare treatment groups (NBI-8027104 versus placebo). Binary efficacy endpoints will be analyzed using Fisher's exact test. An example of the SAS software code is provided below.

[REDACTED]
[REDACTED]
[REDACTED]
[REDACTED]
[REDACTED]
[REDACTED]
[REDACTED]
[REDACTED]

7.3. Interim Analysis

No interim analysis for efficacy is planned for this study.

7.4. Primary Efficacy Endpoint

The primary efficacy endpoint is the log-transformed ratio of SWI at the end of [REDACTED] to baseline during the first hour (60 minutes) of NREM sleep based on centralized video-EEG reading, where baseline is defined as the last value measured prior to intake of study treatment on Day 1.

Inpatient overnight video-EEG using a standard international 10/20 EEG recording setup and concurrent video will be conducted [REDACTED]

[REDACTED] The overnight video-EEG recording will be centrally read and used to compute the endpoints [REDACTED]
[REDACTED]
[REDACTED]

[REDACTED] As an outcome measure of this study to quantify electrographic CSWS activity, the SWI is defined as the percentage of seconds with ≥ 1 spike-wave complex(es) during defined periods of overnight NREM sleep.

Descriptive statistics will be presented for SWI during the first hour of NREM sleep by treatment group and visit for the observed and change from baseline values.

The primary estimand is defined by the following:

Population: All randomized subjects with CSWS defined by study inclusion/exclusion criteria who have taken at least one dose of study drug and have at least one post-baseline efficacy video-EEG assessment.

Variable (or endpoint) to be obtained for each subject: Log-transformed ratio of SWI at [REDACTED] to SWI at baseline

[figure not shown]
[figure not shown]
Population-level summary: Ratio of geometric mean ratio (GMR) of SWI at [REDACTED] to baseline in the NBI-827104 group divided by the GMR of SWI at [REDACTED] to baseline in the placebo group

The least-squares mean treatment difference for this endpoint will be estimated using an ANCOVA model with treatment group as a fixed factor and baseline SWI (log-transformed) as a

covariate. The treatment group difference at [REDACTED] and the 90% CI will be obtained from the ANCOVA model.

The associated summary statistic on a treatment group level is the geometric mean ratio (GMR) of SWI at [REDACTED] to baseline (obtained by exponentiating the mean of the log-transformed ratios). A GMR <1 indicates an improvement from baseline in the treatment group.

Handling of intercurrent events: Treatment-policy approach whereby data is used whether or not an intercurrent event occurs akin to intent-to-treat principle.

7.5. Secondary Efficacy Endpoints

The secondary efficacy endpoints are:

- Ratio of SWI at the end of [REDACTED] to baseline during the first hour (60 minutes) of NREM sleep, based on centralized evaluation
- CaGI-C score at [REDACTED]

- CaGI-C score at [REDACTED]
- CGI-C score at [REDACTED]
- CGI-C score at [REDACTED]
- Change from baseline to [REDACTED] in CGI-S score
- Change from baseline to [REDACTED] in CGI-S score

7.5.1. SWI during the first hour at [REDACTED]

The ratio of SWI at the end of [REDACTED] to baseline during the first hour (60 minutes) of NREM sleep, based on centralized evaluation, will be summarized descriptively by treatment group and visit, and change from baseline analyzed with ANCOVA models similar to those used for the primary endpoint.

7.5.2. CaGI-C Scores at [REDACTED]

The CaGI-C is a 7-point scale and provides a global evaluation of the subject's change in CSWS symptoms since baseline from the caregiver's perspective. If possible, the same person should rate the CaGI-C at all visits (ie, [REDACTED] [or ET]). Subjects can be scored from 1-7: Very much improved (1), Much improved (2), Minimally improved (3), No change (4), Minimally worse (5), Much worse (6), Very much worse (7).

The number and percentage of subjects by CaGI-C categories will be summarized by treatment group and postbaseline visit. In addition, subjects whose CaGI-C score is either a 1 ("Very much improved") or a 2 ("Much improved") will be classified as responders. CaGI-C ordinal categories, as well as binary response status, will be analyzed at [REDACTED] using the methods described in Section 7.2.2 for categorical efficacy endpoints.

7.5.3. CGI-C at [REDACTED]

The CGI-C, which is based on a 7-point scale (range: 1=Very Much Improved to 7=Very Much Worse) requires the clinician to rate the overall change in the subject's CSWS symptoms since the subject started taking the study drug, relative to baseline.

[figure not shown]
The number and percentage of subjects by CGI-C categories will be summarized by treatment group and postbaseline visit. In addition, subjects whose CGI-C score is either a 1 ("Very much improved") or a 2 ("Much improved") will be classified as responders. CGI-C ordinal categories, as well as binary response status, will be analyzed at [REDACTED] using the methods described in Section 7.2.2 for categorical efficacy endpoints.

[figure not shown]
7.5.4. CGI-S at [REDACTED]

[figure not shown]
The CGI-S is a 7-point scale that required the clinician to rate the severity of the subject's illness at the time of assessment (ie, Day 1, and [REDACTED] [or ET]), relative to the clinician's past experience with patients who have CSWS. Subjects can be scored from 1-7: Normal, not at all ill (1), Borderline ill (2), Mildly ill (3), Moderately ill (4), Markedly ill (5), Severely ill (6), Among the most extremely ill patients (7).

[figure not shown]
Number and percentage of subjects by CGI-S categories will be summarized by treatment group and visit. In addition, subjects with at least a 1-point improvement from baseline in CGI-S will be classified as responders. CGI-S ordinal categories, as well as binary response status, will be analyzed at [REDACTED] using the methods described in Section 7.2.2 for categorical efficacy endpoints. Shift tables for CGI-S categories from baseline to [REDACTED] will be presented.

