### 13.10. Efficacy Data

Primary efficacy endpoint:

• Ratio of SWI at the end of to baseline during the first hour (60 minutes) of NREM sleep based on centralized video-EEG reading, where baseline is defined as the last value measured prior to intake of study treatment on Day 1.

The primary endpoint was selected based on the observation of highest SWI during the first NREM sleep phases compared with the last (Bölsterli Heinzle et al., 2014), as well as demonstrated sensitivity and responsiveness in a retrospective review of video-EEG data collected in a patient population of children with EECSWS (Aeby et al., 2005).

Secondary efficacy endpoints:

- Ratio of SWI at the end of to baseline during the first hour (60 minutes) of NREM sleep, based on centralized evaluation.
- Caregiver GI-C and CGI-C scores at the end of
- Change from baseline to the end of in CGI-S scores.

Exploratory efficacy endpoints:

The primary efficacy analyses will be performed using the FAS. The Per-protocol analysis set will be used for supportive analyses.

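### The CGI-S secondary endpoint is change from baseline, but the visible SAP gives no treatment difference or confidence interval for it; adding the Section 7.2.1 ANCOVA alongside the planned tests would supply one.

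*SAP*

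**What the plan says.** Both documents define the endpoint as a change. Protocol 13.10 lists "Change from baseline to the end of in CGI-S scores" (the visit is blacked out), and SAP 7.5 lists "Change from baseline to [REDACTED] in CGI-S score" for two visits.

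SAP 7.5.4 describes CGI-S as a rating of severity when it is assessed, starting on Day 1. It then sets the analysis: "CGI-S ordinal categories, as well as binary response status, will be analyzed at" the visit, by the methods of Section 7.2.2. The binary response is defined from change: "subjects with at least a 1-point improvement from baseline in CGI-S will be classified as responders". Shift tables from baseline are also planned.

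Section 7.2.2 states: "Ordinal categorical efficacy endpoints will be analyzed using the Jonckheere-Terpstra test to compare treatment groups". Binary endpoints go to Fisher's exact test. The visible text mentions no covariate, stratum, effect estimate or interval. The example code is redacted.

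Section 7.2.1, for continuous endpoints, models change from baseline. It says "The model will include the relevant baseline value as a covariate, and treatment group (NBI-827104; placebo"), and "The treatment group difference at the postbaseline visit and the 90% CIs will be obtained from the ANCOVA model". Section 7.5.4 does not refer to it. The introduction to SAP 7 adds a general display rule: "descriptive statistics for observed values and changes from baseline will be presented by treatment group".

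**The concern.** A CGI-S category at a visit is a severity level, not a change. The full-scale test therefore compares the groups on a different variable from the one named as the endpoint. The only hypothesis test that uses change first reduces it to improved by at least 1 point or not. Shift tables and descriptive summaries show change but do not compare the groups with a stated uncertainty.

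Two things are at stake. First, as visible, the plan produces no estimate of the treatment effect on the endpoint it names. In a Phase 2 study of approximately 24 subjects, an estimate with a 90% CI says more than a p-value alone. Second, Day 1 severity is collected but the full-scale test does not use it, which may cost precision.

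The point is specific to CGI-S. CGI-C and CaGI-C are rated as change already, so Section 7.2.2 gives them a test of the quantity that was named.

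**Working it through.** **Text comparison**

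| Item | Place | Content |
|---|---|---|
| Endpoint | Protocol 13.10; SAP Table 1 and 7.5 | Change from baseline in CGI-S |
| Full-scale test | SAP 7.5.4 with 7.2.2 | Visit categories, Jonckheere-Terpstra, no baseline term stated |
| Test of change | SAP 7.5.4 with 7.2.2 | Improvement of at least 1 point, Fisher's exact test |
| Other displays of change | SAP 7.5.4; SAP 7 | Shift tables; descriptive statistics |
| Estimate and CI for change | SAP 7.2.1 only | ANCOVA, not invoked for CGI-S |

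The gap is therefore confined to a between-group estimate of full-scale change.

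**Inputs for size**

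From the documents: two-sided alpha 0.10 (SAP 4.1); approximately 24 subjects at 2:1, made up of 4:2 in the sentinel cohort and 18 at 2:1 in the main cohort (SAP 3.1), hence 16:8. SAP 3.4 expects at least 21 and later at least 18 evaluable subjects, but for SWI. Neither document gives a power, SD, effect or correlation for CGI-S, so there is no plan figure to reproduce.

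Assumed: baseline mean 5; SD 0.9 (range 0.7 to 1.2); mean effect 0.75 points; baseline-visit correlation rho 0.2 to 0.7. Scores are latent bivariate normals rounded and clipped to 1-7.

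**Formulas**

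- Standard error of a chance baseline gap, in SD units: sqrt(1/16 + 1/8) = 0.433. The probability of a gap above 0.5 SD in either direction is 2 × [1 − Φ(0.5/0.433)], about 25%. An unadjusted visit comparison carries such a gap in proportion to rho.
- On a continuous scale, baseline adjustment multiplies the residual variance by 1 − rho²: 0.91, 0.75 and 0.51 at rho 0.3, 0.5 and 0.7.

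**Simulation on the 7-point scale** (10,000 trials per cell; same shift for every treated subject; SD 0.9; 16:8). With two groups, Jonckheere-Terpstra (JT) is a tie-corrected rank-sum test.

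| rho | JT power | ANCOVA power | 90% CI half-width, ANCOVA | Half-width, unadjusted |
|---|---|---|---|---|
| 0.2 | .544 | .548 | 0.70 | 0.69 |
| 0.3 | .541 | .556 | 0.68 | 0.69 |
| 0.5 | .544 | .621 | 0.63 | 0.69 |
| 0.7 | .549 | .731 | 0.55 | 0.69 |

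The ANCOVA interval thus runs from about 1% wider (0.70/0.69 = 1.01) to about 20% narrower (0.55/0.69 = 0.80).

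- *Other SDs.* At rho 0.3, 0.5 and 0.7, JT/ANCOVA is .707/.721, .702/.766 and .714/.860 at SD 0.7, and .384/.396, .384/.444 and .377/.541 at SD 1.2. At SD 0.7 and rho 0.2, ANCOVA loses about 1 point (.711/.700).
- *Fewer subjects.* If CGI-S is available for 18 subjects (assumed 12:6, SD 0.9): .440/.436, .446/.457, .441/.502 and .449/.601 at rho 0.2, 0.3, 0.5 and 0.7.
- *Effect confined to responders.* Keep the 0.75-point mean, but let it come from 40% of treated subjects (0.75/0.40 = 1.875 points each). At 16:8 and SD 0.9, JT/ANCOVA is .374/.366, .379/.382, .390/.415 and .379/.454 at the same four correlations. A second run gave gains of about 3 points at rho 0.5 and 6 to 7 at rho 0.7.
- *Planned responder test.* Fisher's power under the common shift at 16:8, SD 0.9 is .279, .362 and .485 at rho 0.3, 0.5 and 0.7.
- *Size with no effect.* JT .096-.106 and ANCOVA .094-.105, both at the nominal 0.10. ANCOVA 90% CI coverage is .894-.906.

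**Range at 16:8 for a 0.75-point mean effect.** ANCOVA minus JT is about -1 to +2 percentage points at rho 0.2-0.3, 3 to 8 at 0.5 and 6 to 18 at 0.7. At 0.5 and 0.7 the low ends belong to the responder pattern.

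**The case against.** The strongest reply is that nothing in the plan is wrong. CGI-S is a 7-level ordinal scale, and the SAP treats it so throughout: categories, shift tables, a rank-type test, and ordinal summaries by median and range (SAP 4.1). Change is not ignored either, since it is tested as a one-step improvement and tabulated. This all stands.

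A reader might infer that the CGI-S tests are invalid, or that ANCOVA should replace them as the main analysis. The documents support neither inference. The planned full-scale test keeps its size. Which analysis should lead for a 7-level score is a choice on which statisticians differ, and the SAP has made a defensible one.

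It is also fair that the power gain rests on an unknown correlation and on the shape of the effect. At low correlation there is no gain, or a very slight loss. This removes power as the main argument but leaves the missing estimate untouched.

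Finally, the example code in 7.2.2 is redacted and the abbreviation list includes CMH without visible use, so a hidden baseline term cannot be excluded. The point is limited to the visible text. The redaction itself is not a fault.

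**Conclusion.** The point holds at low severity. As visible, the SAP names change in CGI-S as a secondary endpoint but provides no between-group estimate or CI for it, although Section 7.2.1 already contains a suitable model and Day 1 CGI-S is collected. The main benefit is that estimate, and it does not depend on any assumed correlation. The power and precision figures do depend on assumed SD, effect, effect shape and correlation, and should be read as a range. A material power gain needs a correlation of roughly 0.5 or more, which nothing in the documents establishes. The conclusion extends neither to CGI-C and CaGI-C nor to the validity of the planned CGI-S tests.

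**What to change.** Keep the Jonckheere-Terpstra test, the 1-point responder test and the shift tables as planned. Add to SAP 7.5.4:

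> Change from baseline in CGI-S at each analysis visit will also be analyzed with the ANCOVA model of Section 7.2.1 (treatment group as factor, baseline CGI-S as covariate), reporting the treatment difference with 90% CI.

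The cost is one sentence, with no new data or visits and no method the SAP lacks. The downsides are 1 degree of freedom, a 7-level score treated as continuous, and one more analysis without multiplicity adjustment (SAP 7.1). Make the change before database lock, because SAP 4.1 classes analyses defined later as post hoc.
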